Optimizing Immunosuppression Drug Dosing via Phenotypic Precision Medicine
NCT03527238

University of Florida IRB-01 Protocol

TITLE:

Optimizing Immunosuppression Drug Dosing via Phenotypic Precision Medicine

INVESTIGATORS AND STUDY STAFF:

[name], [name], [name], [name], [name], [name], [name] ([name] and [name] at UCLA)

ABSTRACT:

The investigators have developed a computational platform to rapidly identify optimal drug and dose combinations from the innumerable possibilities. By testing this technique termed Phenotypic Personalized Medicine (PPM) in a diverse number of experimental systems representing different diseases, they have found that the response of biological systems to drugs can be described by a low order, smooth multidimensional surface. The main consequence of this is that optimal drug combinations can be found in a small number of tests. This input-output relationship is always based on experimental data, not modeling, and it would lead to a straightforward solution for handling human diversity in drug dosing needs, among other clinical problems. The investigators will test the hypothesis that PPM can be developed and validated for clinical use by conducting a prospective clinical trial to compare the feasibility and efficacy of this approach to standard of care provider dosing. This group has previously used PPM-based optimization to find novel drug combinations in in vitro and in vivo models of cancer and infection. In a published first-in-human study, they compared 4 PPM-dosed patients and 4 control (standard of care dosed) patients. They calculated the tacrolimus dosing regimen using the PPM process and showed significant improvement in variability and a trend toward improved efficacy in achieving goal drug blood-levels. For this application, they aim to show in a larger clinical trial, that PPM is more effective than unaided (standard of care) dosing. This will allow the generation of data to justify a multi-center confirmatory study and to explore a wider array of clinical outcomes to optimize.

BACKGROUND:

The introduction of calcineurin inhibitors like tacrolimus has greatly reduced the incidence of acute rejection and has improved graft and patient survival after transplantation. However, these drugs have narrow therapeutic ranges and serious side-effects. Inter- and intra-individual variability in dosing requirements, particularly across different patient populations, necessitates empirical physician-titrated drug administration that frequently results in deviation from target ranges, particularly during the critical post-operative phase. Multiple studies have shown that high drug level variability is associated with poor long-term outcomes, including rejection and graft loss. As such, there is a clear need for personalized medicine to address post-transplant immunosuppression. However, a robust procedure to achieve personalized coadministration of tacrolimus and other post-transplant drugs has thus far not been available.

Post-transplant immunosuppression provides a challenging model to test any precision medicine platform. Previous studies have sought to personalize tacrolimus dosing using genetics, population pharmacokinetics, and other predictive modeling approaches. However, it is difficult to simultaneously account for the substantial degree of inter- and intra-individual variability in treatment regimens. These differences also lead to health disparities that are not solely attributable to access, socioeconomic, or adherence. Tacrolimus, one of the most widely used immunosuppressants and a mainstay of solid organ transplantation, has a narrow therapeutic index and wide pharmacokinetic variability; it is a substrate of cytochrome P450 and P-glycoprotein (also known as MDR1 or ABCB1), both with genetically variable expression levels in

the intestine and liver. Clearance of tacrolimus is dependent on liver and kidney function, both of which can vary tremendously in the post-transplant setting. Furthermore, all post-transplant patients are on multiple interacting medications. A simple pharmacogenetic algorithm will not be able to respond adequately to the variability.

We have developed a powerful platform that utilizes patient clinical data to construct a Parabolic Response Surface (PRS). The PRS is patient-specific and based on individualized values that represent each patient's response to drug treatment. Examples of this response can be tacrolimus blood trough levels or quantitative markers of organ function or injury. PRS reconciles clinical data into a visual map that enables the immediate identification of optimal drug doses needed to bring drug levels to within the desired range. Importantly, because the PRS process does not require a priori knowledge of disease mechanism, it can efficiently prescribe precise and optimized drug doses despite the frequent changes to patient treatment regimens following transplantation that can have a profound effect on drug metabolism.

SPECIFIC AIMS:

Overall Aim: Prospective randomized clinical trial applying PPM to tacrolimus dosing in liver and/or kidney transplant recipients to show improvement in maintaining drug trough levels within the target range.

Sub-Aim 1: Prospective clinical trial comparing PPM-based dosing with standard of care physician guided dosing in liver and/or kidney transplant recipients to show improvement in time-within-target-range of drug trough levels.

Measures of drug level management will include i) fraction of days outside of target range, ii) fraction of days with large deviations (>2 ng/mL), and iii) ratio of area-under-the-curve outside of target range to total. Clinical measures in both arms will also be monitored to ensure subject safety and correlate trough level maintenance to clinical outcomes.

Sub-Aim 2: Substudy comparing the pharmacokinetics of patients with high variance in tacrolimus dosing with those with low variance.

To examine contributors to variance in tacrolimus dosing, we will measure the pharmacokinetics of a subset of patients in this study and correlate the findings with donor/recipient genetics, changes in drug regimens, and clinical factors such as liver and kidney function. We will use the pharmacokinetic data to interpret the performance of PPM and provide additional validation for our trial.

RESEARCH PLAN:

The aim of this project is to use PPM to uncover valuable and previously unknown information pertaining to patient dose requirements and correlate them with patient clinical and other contextual information. Importantly, because PPM is able to determine patient-specific levels of drug synergism and antagonism, this project is also expected to reveal vital patient subpopulation information in terms of how the modulation of multiple medications may impact tacrolimus levels and/or precision-based measures of immunosuppression at a patient-specific level. In addition, any future discovery of quantitative biomarkers as measures of immunosuppression will serve as a gateway towards even more effective personalized and relevant drug dosing.

Aim: Prospective randomized clinical trial applying PPM to tacrolimus dosing in liver and/or kidney transplant recipients to show improvement in maintaining drug trough levels within the target range.

Sub-Aim 1: Prospective clinical trial applying PPM to tacrolimus dosing in liver and/or kidney transplant recipients to show improvement in management of drug trough levels. This sub-aim constitutes the crux of the proposal. Its key objectives are: 1) to ensure the safety of the subjects; 2) to test the performance of PPM in guiding tacrolimus dosing in order to keep patient drug levels

within target range more frequently, lead to fewer days out of range, and result in smaller deviations from the target range than the standard of care.

Adult patients who have undergone deceased donor liver and/or kidney transplantation will be recruited and randomized 1:1 to standard of care physician-guided dosing or PPM-guided dosing. Patients with contraindications to tacrolimus will be excluded. Following transplantation, patients will be started on a standard of care medication regimen including tacrolimus. For the first 72 hours tacrolimus will be dosed per standard of care. This allows enough data points to be gathered to allow PPM prediction. Blood tacrolimus trough levels will be taken daily. For standard of care subjects, a senior clinical pharmacist will determine the subsequent doses in consultation with the attending surgeon on call. For PPM subjects, de-identified data consisting of the daily treatment regimen details including drugs already administered, drugs to be administered, and hemodialysis or any other procedures to be performed will be sent to the PPM team at UCLA. Following analysis, the PPM team will suggest a tacrolimus dose for clinician (attending surgeon on call) approval prior to administration. In the rare instance that the UCLA team cannot arrive at a recommendation, then the subject will receive the standard of care (physician-guided) tacrolimus dose. Patients will remain on the trial until discharge from the hospital at which point they will all revert to standard of care dosing. Outcome measures will include i) fraction of days outside of target range, ii) fraction of days with large (> 2 ng/mL) deviations, and iii) ratio of area-under-the-curve outside of target range to total. Clinical safety and efficacy measures will also be monitored to ensure subject safety and to correlate trough level maintenance to clinical outcomes. These include adverse events such as neurotoxicity [documented seizures, clinically significant tremors, or imaging-confirmed posterior reversible encephalopathy syndrome (PRES)], nephrotoxicity (biopsy proven acute kidney injury or calcineurin toxicity, anuria or oliguria requiring dialysis), biopsy-proven rejection, need for repeat steroid pulse, graft loss, or death.

Statistical Analysis. Comparative analysis of the effectiveness of PPM dosing will be assessed using area-under-the-curve and variance analysis as in sub-aim 1 above. Based on our preliminary results thirty patients per group will provide greater than 90% power ($\alpha = 0.05$) to show a difference in a two-tail test.

Feasibility, Anticipated Challenges and Proposed Solutions. The UF transplant program performs more than 150 adult liver and/or kidney transplant operations per year. This allows us to complete recruitment in less than 6 months. We do not anticipate major challenges; [name] has substantial experience working on the clinical validation of PPM. We have already successfully performed a prospective pilot study with the same protocol. Because of this we have an established protocol that is conducive to markedly improving the treatment outcomes of patients that participate in the study.

Sub-Aim 2: Comparing the pharmacokinetics of patients with high variance in tacrolimus dosing with those with low variance.

Studies in kidney transplant recipients have indicated that cytochrome P450 CYP3A5 genotype and hematocrit account for more than 60% of variability in tacrolimus pharmacokinetics. Data in liver transplant patients is less well characterized but the unexplained variability is likely higher. To examine contributors to variance in tacrolimus dosing, we will measure tacrolimus pharmacokinetics in this study and correlate the findings with donor/recipient genetics, changes in drug regimens, and clinical factors such as liver and kidney function. For each subject, at least three blood samples (pre-dose and 2 and 6 hours after the dose) will be collected on study days 2, 7, and 14. We will use these pharmacokinetic data to interpret the performance of PPM predictions and provide additional validation for our trial. Genotyping of each donor and recipient

will be performed for CYP3A5 and P-glycoprotein to look for their contribution to variance in pharmacokinetics. Both one- and two-compartment models will be evaluated.

Statistical analysis. Similar to the previous sub-aim, comparisons between the two groups will be performed using either the two-tailed Welch's t-test or Student's t-test. For nonparametric (non-normal) distributions, a two-tailed Levene's test will be used to compare variances, and a two-tailed Wilcoxon Rank Sum test will be used to compare medians. The number of subjects in this study is similar to that in the study by Gerard et al in their approach to building a model for determination of tacrolimus trough blood concentrations.

Data Safety Monitoring Plan. The Principal Investigator (PI) will be responsible for ensuring participants' safety on a daily basis. Given the low risk status of this study with minimal impact on patient care, a Data and Safety Monitoring Board will not be required. Furthermore, each liver/kidney transplant patient is closely followed by a large group consisting of the clinical transplant team (surgeons, hepatologists, pharmacist, nurse coordinators) and the transplant administrative team (transplant program managers and quality officers). One-month, one-year, and three-year outcomes are monitored closely and reporting on patient quality is mandated by the United Network for Organ Sharing (UNOS). Dedicated statisticians in the transplant program monitor real-time outcomes and report them in weekly emails and monthly quality meetings.

A Data Safety Monitoring Board will additionally be appointed. It will include a transplant hepatologist, a transplant nephrologist, and a biostatistician not involved in the study. We will perform an interim analysis comparing the occurrence of i) biopsy-proven rejection episodes, and ii) fraction of days with large (> 2 ng/mL) deviations after ten patients have been randomized into each arm (twenty total subjects). The board will meet after enrollment of 10 patients into each arm (to evaluate the interim analysis) and then every six months thereafter until study completion. The study will be stopped in the event there is a significant unacceptable difference between the two groups. The biostatistical consulting service at the CTSI will assist in monitoring study enrollment, safety signals, and achievement of targets.

Protection of patient medical records: To ensure that patient information is de-identified/anonymized, we will abstract all data (images, lab, clinical data etc.) onto a page or file with only the anonymization codes with no personal identifiers or utilize protocols/programs that will be able to redact the personal identifiers when uploading them as data for study. The code key will only be available to the Project PI and authorized personnel and kept in a secure, locked location. Upon completion of the study, this coded template/anonymization key will be discarded according to regulations. The PI will oversee this task.

POSSIBLE DISCOMFORTS AND RISKS:

Risks of PPM-guided dosing of therapeutic agents to optimize patient-specific immunosuppression include:

- The administration of a drug dose that varies from those given based on clinical practice. This may result in over-dosing or under-dosing. The risks of chronic over-dosing include altered mental status and renal injury. The risks of chronic under-dosing include possible rejection. Both of these risks are mitigated by the fact that blood drug levels are tested daily and deviations will be corrected.
- For Sub-Aim 2, additional blood draws will need to be performed (2 and 6 hours after the dose), on postoperative days 2, 7, and 14. (The pre-dose blood draw is standard of care.)

- Patient medical records will need to be accessed during the study. Therefore, there is a risk of exposure of PHI. Patient-record access and subsequent anonymizing and de-identification of records will be implemented (as indicated above).

Protection Against Risks: The PPM process is not automated. PPM-suggested doses are always based on implicit limits set by the clinical team so that doses will always be within clinically-relevant levels. Most importantly, the administered dose will always be selected by the supervising physician following consultation with the PPM team.

The blood draws will be performed by trained phlebotomists and will not exceed 7 mL per blood draw for a total of 42 mL over two weeks at maximum.

POSSIBLE BENEFITS:

The subjects themselves may or may not benefit from being part of this study. The PPM process has the potential to optimize tacrolimus dosing for the patients on the treatment arm. For the population at large, the ability to definitively optimize dosing will enable the accurate correlation of genomic factors with dosing trends. This may ultimately help eliminate health disparities in not only transplantation but other indications as PPM is broadly applicable and scalable.

Importance of Knowledge to Be Gained: While it is well known that dosing trends vary between subpopulations based on demographic or pharmacogenomic profiles, it has been challenging to definitively construct accurate and robust subpopulation-specific regimens due to the previous inability to correlate genomic or ethnic information with dose response. The application of PPM that will result in individualized and optimized regimens to be developed for each patient in this study will allow the investigators to correlate information in a way that was previously not possible. This will open new doors to improving treatment outcomes in the form of graft/patient survival for transplant immunosuppression, or other indications in oncology, infectious diseases, and other applications.

CONFLICT OF INTEREST:

None.

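### The plan states no stratification by organ and names only unadjusted tests; an organ term, with stratified randomization if still possible, is a modest and inexpensive gain in precision

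*Combined protocol and SAP*

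**What the plan says.** The design paragraph of Sub-Aim 1 says that adults who have had "deceased donor liver and/or kidney transplantation will be recruited and randomized 1:1 to standard of care physician-guided dosing or PPM-guided dosing". The document gives no stratification factor, block scheme or randomization method, and no expected mix of liver, kidney and combined recipients.

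The Sub-Aim 1 analysis text says that effectiveness "will be assessed using area-under-the-curve and variance analysis as in sub-aim 1 above". That cross-reference points back to its own sub-aim. No covariate is named, and the variance analysis is not defined. The sample size statement is that "thirty patients per group will provide greater than 90% power" at a two-sided 0.05 level, with no effect size or SD.

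Tests are named only under Sub-Aim 2: "Similar to the previous sub-aim, comparisons between the two groups will be performed using either the two-tailed Welch's t-test or Student's t-test". For non-normal data the same paragraph adds that "a two-tailed Levene's test will be used to compare variances", with a Wilcoxon rank sum test for medians. They reach Sub-Aim 1 only through the opening words of that sentence.

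On organ, the Background says: "Clearance of tacrolimus is dependent on liver and kidney function, both of which can vary tremendously in the post-transplant setting". Sub-Aim 2 says: "Data in liver transplant patients is less well characterized but the unexplained variability is likely higher". No outcome is given by organ.

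**The concern.** Organ is fixed before randomization and easy to record, and the protocol's own pharmacology suggests it may predict how well troughs stay in range. If so, leaving it out of the comparison puts between-organ variation into the error term. With 30 per arm and no stratification, one arm may also receive noticeably more liver recipients by chance.

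At stake are precision and the credibility of a result that could be put down to organ mix. Validity is not at stake: under 1:1 randomization the unadjusted comparison holds its error rate on average.

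**Working it through.** **Inputs from the documents:** 30 per arm, 1:1, two-sided 0.05, power above 90% (Sub-Aim 1). **Assumed, because the documents give no figure:** liver share 20 to 50%; organ explaining 0 to 20% of outcome variance (R²).

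**1. The plan's power figure.** It cannot be reproduced without an effect and an SD, so I solved for the effect it implies. With noncentrality λ = d√(30/2) and 58 df, 90% power needs d = 0.851, so λ = 0.851 × 3.873 = 3.297. (Normal approximation: d = (1.960 + 1.282)√(2/30) = 0.837.)

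**2. Power for means with an organ term.** Hold d at 0.851 total SDs. With organ balanced across arms, the residual SD is √(1 − R²), so λ = 3.297/√(1 − R²), with 57 df. The last two columns are simulated (60,000 trials per setting, 30% liver, normal outcomes, HC2 standard errors for the organ model).

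| R² | λ | Balanced, organ term | Not stratified, organ term | Not stratified, Welch |
|---|---|---|---|---|
| 0% | 3.297 | 90.0% | 89.5% | 90.0% |
| 2% | 3.330 | 90.5% | 89.8% | 89.8% |
| 5% | 3.382 | 91.4% | 90.8% | 89.8% |
| 10% | 3.475 | 92.7% | 92.2% | 90.0% |
| 20% | 3.686 | 95.2% | 94.9% | 89.8% |

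Most of the gain comes from the organ term. Adjusting without stratifying gains nothing material at R² of 2% or less. If organ is irrelevant, it costs about 0.5 to 0.8 points.

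**3. Chance imbalance.** With arms fixed at 30/30 and K liver recipients among 60, the number X in one arm is hypergeometric(60, K, 30), and the gap in liver share is |2X − K|/30. For K = 12, 18, 24 and 30 (20, 30, 40 and 50% liver), P(gap ≥ 20 points) = 10.4, 15.8, 18.7 and 19.6%. If the mix itself also varies, these become 7.5, 12.0, 14.7 and 15.5%. With organ-stratified blocks of 4, the largest simulated gap was 6.7 points.

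**4. Type I error (R² = 10%, 20 to 50% liver, 20,000 trials per setting).**
- Not stratified: Welch 4.8 to 5.0%; organ model 4.9 to 5.0%.
- Stratified: Welch 3.7 to 4.3%, which is conservative; organ model 4.8 to 5.2%.
- Bounded, skewed outcome (fraction of 10 days), organ model: 4.6 to 5.3%.

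**5. A between-patient variance comparison, if one is intended.** Median-centred Levene test, 30 per arm, 30% liver in each arm, normal data, 20,000 trials. The first three rows are for organ explaining 5, 10 and 20% of control-arm variance.

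| Assumed PPM effect | Pooled Levene | Levene on organ residuals |
|---|---|---|
| Halves SD within organ; organ shift unchanged | 82, 74, 54% | 88, 89, 88% |
| Halves total SD; organ shift unchanged | 90, 90, 91% | 94, 98, 100% |
| Halves SD within organ and the organ shift | 90, 90, 91% | 88, 88, 87% |
| Halves SD; no shift; liver SD 1.25, 1.5, 2 times kidney SD | 89, 88, 82% | 88, 86, 80% |

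Adjustment thus ranges from a large gain to a loss of up to about 4 points. Regressing the absolute residuals on arm and organ gives about 88, 87 and 85% in the last row and the same as the residual Levene test elsewhere.

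**The case against.** The strongest case against is that this is a preference. No organ effect on the outcomes is documented. The Sub-Aim 2 remark concerns pharmacokinetic variability, and daily titration may remove much of any organ difference. The gain for means is 0 to about 5 points over an assumed range. Stratified blocks have their own cost: the attending surgeon approves PPM doses and is consulted on standard ones, so allocation is visible, and short blocks make upcoming assignments easier to guess. All of this stands. It limits the size of the point and rules out very short blocks. It does not favour unadjusted tests, since adjustment costs less than a point when it is useless.

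Three stronger readings are tempting, and the documents do not support them:

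- **Pooling organs biases the comparison.** Randomization protects it on average. Given a gap of 20 points or more and R² of 10%, Welch rejects a true null 7.5 to 8.1% of the time, but the overall rate stays at 5%.
- **Organ mixing ruins the power of the variance comparison.** The Abstract says the pilot "showed significant improvement in variability and a trend toward improved efficacy in achieving goal drug blood-levels", which makes this attractive. The fall to 54% needs PPM to halve only the within-organ SD and leave the organ shift whole. At R² of 20%, the total SD ratio is then 1/√(0.8/4 + 0.2) = 1.58, not 2, so much of the fall reflects a smaller effect. The variance analysis is also undefined, and the pilot's variability may be within patients, where a patient-level organ offset need not enter.
- **The 20-patient interim could stop the trial wrongly because of organ imbalance.** The Data Safety Monitoring Plan names no interim test, so no such probability can be given.

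**Conclusion.** The point holds as a modest improvement in precision. The plan states no stratification factor and names only unadjusted tests; that is silence about stratification, not a declared decision against it. For means at the 90%-power effect, an organ term with balanced allocation yields 0 to about 5 points for R² from 0 to 20%. Stratification largely removes a 10 to 20% chance of a 20-point gap in liver share. For variances the direction of the effect is uncertain, and no gain is claimed. Everything rests on an organ mix and an organ effect that the documents do not quantify; if organ is not prognostic, there is nothing to gain. The stated power of more than 90% is neither confirmed nor refuted here. The change is worth making because it costs little; confidence is moderate.

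**What to change.** - **Main comparison.** For each of the three Sub-Aim 1 outcomes (share of days out of range, share of days with deviations above 2 ng/mL, share of the area under the curve that lies out of range), prespecify a linear model of the patient's value on arm and organ, with HC2 robust standard errors. Code organ as any liver or kidney alone, so that combined recipients do not form a very small group. Use a van Elteren test stratified by organ as sensitivity analysis.
- **Randomization, if enrolment has not begun.** Stratify by the same two organ groups, with concealed and randomly varying block sizes and no blocks of 2. Keep the organ term in the analysis, since stratifying without adjusting makes the test conservative.
- **If enrolment has begun.** Prespecify the organ-adjusted analyses alone, before outcomes are compared by arm.
- **Variance.** State whether the variance analysis is between or within patients. If between, add a regression of absolute residuals on arm and organ as sensitivity analysis only.

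The cost is a second randomization list, one model term, some predictability of allocation where arms are visible to the treating team, and about 0.5 to 0.8 points of power for means if organ is not prognostic and only adjustment is used. With stratification that loss is about 0.02 points.

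### Outcomes (i)–(iii) and the interim large-deviation measure have no first counted day; if days before arm-specific dosing are counted, the arm contrast is diluted and power is lost

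*Combined protocol and SAP*

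**What the plan says.** Research Plan, Sub-Aim 1, describes a common opening period: "For the first 72 hours tacrolimus will be dosed per standard of care". Its purpose is given next: "This allows enough data points to be gathered to allow PPM prediction". Troughs are drawn daily, and the arms diverge only in the doses that follow. The end of observation is clear: "Patients will remain on the trial until discharge from the hospital at which point they will all revert to standard of care dosing".

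The outcomes are then listed: "Outcome measures will include i) fraction of days outside of target range, ii) fraction of days with large (> 2 ng/mL) deviations", and as (iii) the ratio of the area under the curve outside the target range to the total. The Specific Aims give the same list. The Data Safety Monitoring Plan reuses outcome (ii) at the interim look, after ten patients have been randomized to each arm. None of these places gives a first counted day, and none says when randomization takes place relative to the 72 hours.

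The Statistical Analysis paragraph of Sub-Aim 1 says effectiveness "will be assessed using area-under-the-curve and variance analysis as in sub-aim 1 above", but no window is defined above it. The tests are named only under Sub-Aim 2: "Similar to the previous sub-aim, comparisons between the two groups will be performed using either" a Welch or Student t-test, with rank-sum and Levene alternatives. No baseline adjustment is mentioned.

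**The concern.** For an outcome that is a fraction of days, the denominator is part of the definition. Two analysts could follow this plan faithfully and compute different values of (i)–(iii), one from entry and one from the first day on which PPM could have affected a trough.

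The choice matters because Sub-Aim 1 is meant to test how well PPM guides dosing. Days on which PPM guided nothing cannot inform that question. If they are counted, they pull the two arms' averages together, and a null result could partly reflect those days. At the interim look, the same dilution would partly mask an excess of large deviations under PPM. The early troughs would be more useful as a baseline, and the plan already collects them.

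**Working it through.** **1. The plan's own figure.** Inputs from Sub-Aim 1, Statistical Analysis: 30 per group, two-sided alpha 0.05, power above 90%. The effect, SD, powered outcome and window are not given. The preliminary data described in the Abstract are 4 against 4 patients, without means or SDs. Solving backwards, 90% power needs a standardized difference of (1.960 + 1.282) × √(2/30) = 3.242 × 0.2582 = 0.837 (0.851 with the noncentral t). The claim can be neither reproduced nor refuted.

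**2. Dilution of a day fraction.** With daily troughs, 72 hours covers about three days. For an assumed stay of L days, all counted, the expected difference is the post-72-hour difference × (L−3)/L:

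- L=14: 11/14 = 0.79
- L=10: 7/10 = 0.70
- L=7: 4/7 = 0.57

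Three days is close to an upper bound, because patients are recruited after transplantation at an unstated time. Counting from day 2 gives (L−3)/(L−1), which is 11/13 = 0.85 at L=14. Counting from day 3 gives 11/12 = 0.92.

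**3. Power for a day fraction (simulation).** All model inputs are assumptions: control out-of-range probability 0.6 at the average patient; patient SD 1 on the logit scale; correlation 0 to 1 between a patient's early and late levels; PPM effect only from day 4; Welch test on patient fractions. A log-odds shift of −1 gives a mean difference of about 20 points, and −1.5 gives about 30. Ranges span the correlation and simulation error.

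| 30 per arm | Whole stay | Post-72-hour |
|---|---|---|
| 20 points, L=14 | 73–84% | 88–89% |
| 20 points, L=10 | 58–74% | 82–83% |
| 20 points, L=7 | 38–52% | 72–73% |
| 30 points, L=14 | 97–99% | nearly 100% |
| 30 points, L=10 | 90–97% | 99% |
| 30 points, L=7 | 71–84% | 97% |

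With no effect, rejection rates were 4.7–5.3%, so both windows give valid tests. With later entry (20 points, L=14), power is 78–86% counting from day 2 and 83–88% counting from day 3, against 88–89%.

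**4. Other measures.** The factor (L−3)/L is not exact for outcome (iii), because the first 72 hours are weighted by the area they contribute. Assume a band of 8–12 ng/mL, a late log-SD of 0.40 against 0.25, and an early mean of 5, 10 or 14. The AUC-ratio effect retained is then 0.87, 0.80 or 0.73 at L=14, and power is 86–94% against 98%. At L=10 power is 65–82% against 94–95%. The loss is not universal: in this model, outcome (ii) with early mean 5 at L=14 gives 89.0% against 89.1%.

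**5. Interim look.** With 10 per arm, a 20-point excess of large deviations and p<0.05 used only as an illustration, power is 31–38% against 42% at L=14 and 24–31% against 37–38% at L=10.

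**6. Baseline adjustment.** Adding the first-72-hour fraction as a covariate to the post-72-hour analysis (20 points) gives 88, 90 and 95% at L=14 for correlations 0, 0.5 and 1, and 83, 85 and 90% at L=10. The cost at correlation 0 is at most about 1 point.

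**The case against.** The strongest reply is that the plan already points to a post-72-hour window. It describes the opening period as data gathering for the algorithm and frames the analysis around the effectiveness of PPM dosing. That leaning is real, but it does not settle the denominator. Some text leans the other way: Sub-Aim 2 says pharmacokinetic samples "will be collected on study days 2, 7, and 14", while Possible Discomforts and Risks calls the same draws postoperative days. Study days therefore appear to include the shared period. This is weak evidence, since it concerns sampling and not the outcomes.

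The second reply concerns size, and much of it stands. Stay, effect and SDs are all assumed. The largest losses come from L=7, and the documents do not support that as typical; the only horizon they give is two weeks of sampling. The 20-point scenario does not reach the plan's 90% even with the better window. The 30-point scenario does, and there the loss is small at stays of 10 days or more. Later entry shrinks it further.

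A reader might infer that the power above 90% is wrong. The documents do not support that. The pilot's window and effect are not reported, and Feasibility says "We have already successfully performed a prospective pilot study with the same protocol", so any dilution may already be in the effect used. A reader might also infer that a whole-stay analysis is invalid. It is not: it is a valid randomized comparison, but a less sensitive one for the effect of PPM dosing.

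At the interim look, ten per arm is the main limit. Rejection is also compared and levels are checked daily, so the gain there is marginal.

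**Conclusion.** The point holds as a gap in the outcome definitions with a conditional cost. No section gives the first counted day for (i)–(iii) or for the interim measure, or the time of randomization. If days before arm-specific dosing are counted, up to three of L days carry no contrast. In the illustrative model with a 20-point effect and all three shared days counted, that costs roughly 5 to 15 points of power at L=14 and 9 to 24 at L=10. The cost is greater for shorter stays, smaller for larger effects or later entry, and little or none in some scenarios for outcome (ii). These sizes rest on assumed inputs; the omission does not. It should be fixed before outcome data are examined, because the remedy is cheap and the choice of window changes the endpoint.

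**What to change.** 1. Compute (i)–(iii) from one fixed study day through discharge: the day of the first daily trough after hour 72 that can reflect arm-specific dosing. Use the same day in both arms, whether or not a PPM recommendation was available. If the first post-72-hour trough is drawn before that dose, start the next day. Report the whole stay as a sensitivity analysis.
2. Use the same window for the interim large-deviation measure.
3. Adjust the arm comparison for the first-72-hour out-of-range fraction or mean absolute deviation.
4. State when randomization occurs, and the window and effect behind the power above 90%.

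The cost is wording, one covariate and one reporting line; no new samples and no dosing change are involved. Each patient contributes a few fewer days, which the post-72-hour power figures already reflect for a day-4 start. Starting at day 5 when day 4 was already informative costs about 1 further point at L=14 and 3 at L=10. Patients discharged before the window opens do not inform efficacy; report them by arm and keep them in the safety set. The covariate costs about 1 point of power if early and late troughs are uncorrelated.
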